CLINICAL PROTOCOL

CTIX-BRI-205

Phase 2, Multi-center, Randomized, Double-blind, Placebo-controlled Study to Evaluate the Efficacy and Safety of Brilacidin Oral Rinse Administered Daily for 7 Weeks in Attenuating Oral Mucositis in Patients with Head and Neck Cancer Receiving Concurrent Chemotherapy and Radiotherapy

Document type:	Clinical Protocol - Amended
Version number:	1.9
Version date:	23 August 2017
NCT number:	NCT02324335

CONFIDENTIALITY STATEMENT

The information provided in this document is strictly confidential. This information may not be used, published or disclosed without prior written approval from Innovation Pharmaceuticals Inc. (formerly Cellceutix Corporation)

PROTOCOL SYNOPSIS

Name of Sponsor/Company: Innovation Pharmaceuticals Inc. (formerly Cellceutix Corporation)
Name of Finished Product: Brilacidin Solution, 50 mg/ml (free base)
Name of Active Ingredient: Brilacidin tetrahydrochloride
Title of Study: Phase 2, Multi-center, Randomized, Double-blind, Placebo-controlled Study to Evaluate the Efficacy and Safety of Brilacidin Oral Rinse Administered Daily for 7 Weeks in Attenuating Oral Mucositis in Patients with Head and Neck Cancer Receiving Concurrent Chemotherapy and Radiotherapy
Study Centers: Approximately 20 sites in the United States will participate in the study
Number of Subjects Planned: Approximately 60 subjects with head and neck cancer receiving concurrent chemotherapy and radiotherapy
Study Duration per subject: Approximately 17 weeks
Phase of Development: 2
Primary Objective(s): 
• To evaluate the efficacy of topically applied brilacidin administered three times daily by oral rinse for approximately 7 weeks (treatment week is defined as a 7-day period, irrespective of the day of the week that the 7-day period begins) compared to placebo in reducing the incidence of severe OM (defined as grade 3 or 4 on the WHO Oral Mucositis scale, WHO Grade ≥ 3) in subjects with head and neck cancer (HNC) receiving concomitant chemoradiation therapy (CRT).• To evaluate the safety and tolerability of topically applied brilacidin administered three times daily by oral rinse for approximately 7 weeks (treatment week is defined as a 7-day period, irrespective of the day of the week that the 7-day period begins).

Secondary Objectives:

- To evaluate the efficacy of topically applied brilacidin in reducing the duration of severe OM (WHO Grade ≥ 3) in subjects with HNC receiving concomitant chemoradiation therapy.
- To evaluate the efficacy of topically applied brilacidin in delaying the onset of severe OM (WHO Grade ≥ 3) in subjects with HNC receiving concomitant chemoradiation therapy.

Design and Methodology:

The study is a Phase 2, randomized (1:1 ratio), double-blind, placebo-controlled, 2-arm trial to be conducted in patients receiving chemoradiation for the treatment of squamous cell carcinoma of the oral cavity, oropharynx, hypopharynx, or supraglottic larynx.

Patients with this diagnosis whose anticipated treatment includes chemoradiation therapy (CRT) and who consent to participate will enter a screening period of up to 45 days prior to the anticipated initiation of CRT. If eligible, subjects will be randomized to one of the two blinded study treatments and will enter the treatment phase of the study (approximately 11 weeks in duration).

For entry into the study, eligible patients will have recently-diagnosed (in the previous 6 months), pathologically-confirmed, non-metastatic squamous cell carcinoma of the oral cavity, oropharynx, hypopharynx, or supraglottic larynx. Tumor staging for eligibility, using AJCC Tumor Staging Guidelines, or as determined by institutional tumor board review may be determined from scans (CT, PET, and/or MRI) obtained within 120 days prior to consent for screening. Scan interpretation should follow Response Evaluation Criteria in Solid Tumors (RECIST) Version 1.1 criteria (Appendix E).

Patients must be scheduled to receive a continuous course of intensity-modulated radiation therapy (IMRT) with a minimum cumulative dose of 55 Gray (Gy) and maximum cumulative dose of 72 Gy over approximately 7 weeks (treatment week is defined as a 7-day period, irrespective of the day of the week that the 7-day period begins). Planned radiation treatment fields must include at least two oral sites (buccal mucosa, floor of mouth, ventral/lateral tongue, soft palate). The treatment plan must include chemotherapy with cisplatin administered in standard weekly (30-40 mg/m²) or approximately every 21 days (80-100 mg/m²) regimens. No other chemotherapy is allowed during radiotherapy unless intolerance to cisplatin is demonstrated during study participation. In this case, with medical monitor approval, carboplatin may be substituted.

Eligible subjects will be randomized to receive one of the following study drug regimens during participation in the study (1:1 ratio):

Arm A: Placebo (WFI) [oral rinse tid]

Arm B: Brilacidin 3 mg/mL in WFI [oral rinse tid]

The study drug will be administered as an oral rinse three times daily (approximately 6 hours between oral rinses) beginning on the first day of radiotherapy and continuing each day (including weekends) until the completion of the course of chemoradiation. The

subject will be instructed to use the study oral rinse three times each day with approximately 6 hours between each use, whenever possible. Subjects will be instructed to perform the oral rinse for 1-minute and *spit out the rinse after each use, avoiding swallowing any of the rinse*. The first use of oral rinse on the first day of study drug treatment must be witnessed by a member of the study staff. Subjects will be told not to eat, brush their teeth, chew gum, or suck on hard candy, cough drops, etc., for at least 10 minutes before each oral rinse. A subject should rinse his/her mouth with plain water prior to administering the oral rinse. Subjects will be told not to eat, drink, brush their teeth, chew gum, or suck on hard candy, cough drops, etc., for 30 minutes following each use of the oral rinse. Subjects who use allowed non-study oral rinse(s) (i.e., Gelclair®, saline solutions) during the study period should ensure that the study oral rinse is used at least 60 minutes after use of a non-study oral rinse and that a non-study oral rinse is not used until at least 60 minutes after use of the study rinse.

Note: Although chemoradiation is complete (i.e. the end of radiation therapy (ERT) visit has occurred), subjects are to complete the full 7 days of study drug for Week 7.

The treatment phase of the study will include: (1) the period of RT treatment with concomitant chemotherapy and (2) all assessments occurring after the last dose of RT, through and including a Week 4 Post-RT follow-up visit (the EOS visit).

- During the CRT treatment period, subjects will be assessed twice weekly for the presence and severity of OM by trained evaluators using the WHO grading scale for OM. Subjects will complete a daily study diary (including weekend days). The diary contains Question 2 of the Oral Mucositis Daily Questionnaire (OMDQ), a record of daily analgesic use for mouth and/or throat pain, a record of the study drug oral rinses performed each day, and the subject's assessment of mouth sensations. The diary will be reviewed by a member of the study staff each day during the first week (at least 5 days) of study treatment to ensure that the subject is appropriately completing the diary. If subject diary completion is satisfactory, then the diary will be reviewed at least once weekly during the remainder of the study. At weekly intervals (on the same day of each week), subjects will complete the FACT-H&N instrument to record quality of life responses.
- Single samples (venous blood) for assessment of brilacidin plasma concentrations will be obtained from each subject at weekly intervals during the CRT treatment period. These blood samples may be obtained at the time of the venipuncture for clinical laboratory tests as specified by the protocol.
- For those subjects who have consented to gene analysis, samples of venous blood will be obtained at baseline, during week 3, and on the last day of radiation.
- All subjects will be evaluated at 1 week after RT completion (or withdrawal from the study) for assessment of the presence and severity of OM and other safety assessments. Subjects having an WHO OM Grade ≥ 2 at this post-treatment visit will return to the clinic at weekly intervals until mucositis resolves to WHO OM Grade < 2 ; subjects having a WHO OM Grade ≤ 1 may be followed by weekly phone call instead. During the post-RT period, subjects will continue to complete the daily study diary

that contains Question 2 of the OMDQ as well as recording analgesic use and subjects will complete the FACT-H&N QOL instrument weekly until 4 weeks (\pm 2 days) post-RT. In most instances the last study related visit, the End of Study (EOS) visit, will be at Week 4 post-RT.

Patient Eligibility:

- Patients with recently diagnosed (within previous 6 months), pathologically-confirmed, non-metastatic squamous cell carcinoma of the oral cavity, oropharynx, hypopharynx, or supraglottic larynx.
- Patients scheduled to receive a continuous course of IMRT over approximately 7 weeks (treatment week is defined as a 7-day period, irrespective of the day of the week that the 7-day period begins) with a minimum cumulative dose of 55 Gray (Gy) and maximum cumulative dose of 72 Gy. (IMRT is typically administered as 35 separate radiation treatments).
- Planned radiation treatment fields must include at least two oral sites (buccal mucosa, floor of mouth, ventral/lateral tongue, soft palate). The treatment plan must include chemotherapy with cisplatin administered in either a standard weekly (30-40 mg/m²) or approximately every 21 days (80-100mg/m²) regimen. No other chemotherapy is allowed during radiotherapy unless intolerance to cisplatin is demonstrated. In this case, with medical monitor approval, carboplatin may be substituted.

Inclusion Criteria:

1. Willing and able to read, understand, and sign an informed consent form (ICF) for the study approved by the Investigator's local or a central Institutional Review Board (IRB) or Independent Ethics Committee (IEC) prior to the initiation of any study-related procedures.
2. Males or females aged \geq 18 years on day of consent.
3. Have recently-diagnosed (within previous 6 months pathologically-confirmed, non-metastatic squamous cell carcinoma of the oral cavity, oropharynx, hypopharynx, or supraglottic larynx. The treatment planned will utilize CRT therapy as first line non-surgical treatment. Scans (CT, PET, and/or MRI) obtained within 120 days prior to consent for screening can be used to determine the patient's eligibility.

Note: Post-surgical subjects may be enrolled provided any head/neck surgical sites (including sites of dental extractions) are sufficiently healed.

4. Have a plan to receive a continuous course of conventional external beam irradiation delivered by intensity-modulated radiation therapy (IMRT) as single daily fractions of 2.0 Gy to 2.2 Gy with a cumulative radiation dose \geq 55 Gy and \leq 72 Gy. Planned radiation treatment fields must include at least two oral sites (buccal mucosa, floor of mouth, ventral/lateral tongue, soft palate)

Note: The independent RTQA consultant must confirm that the planned radiation treatment meets the protocol criteria.

5. Have a plan to receive a standard cisplatin chemotherapy regimen administered weekly (30-40 mg/m²) or approximately every 21 days (80-100 mg/m²)
6. Have an Eastern Cooperative Oncology Group (ECOG) Performance Status of 0, 1, or 2. However, potential subjects with an ECOG Performance Status of 3 may be enrolled provided their condition does not preclude performing the actions required by study participation (e.g. opening medication bottles, swishing the oral rinse and spitting out, completing or participating in completion of daily diaries and FACT-H&N forms).
7. Have adequate hematopoietic, hepatic, and renal function at screening:
 - a. Hematopoietic function
 - i. Hemoglobin \geq 9 g/dL
 - ii. Absolute neutrophil counts (ANC) \geq 1.5 x 10³/uL
 - iii. Platelet count \geq 100 x 10³/uL
 - b. Hepatic function
 - i. Total bilirubin \leq 1.5 times the upper limit of normal (ULN)
 - ii. Alanine aminotransferase (ALT) and aspartate aminotransferase (AST) \leq 2.0 times the ULN
 - c. Renal function
 - i. Either a serum creatinine concentration within the site laboratory's normal limits or a calculated creatinine clearance $>$ 60 mL/min
8. Urine or serum pregnancy test: negative for female patients of childbearing potential. If pregnancy test is performed more than 10 days prior to the start of radiotherapy, the test must be repeated prior to Day 1.
9. Female subjects with reproductive potential must agree to use reliable means of contraception (e.g., abstinence, double barrier method, oral/implantable/transdermal contraception, Depo-provera, intrauterine device, or physical barrier) throughout study participation and for 90 days after the last use of study oral rinse.
A female is considered of reproductive potential unless she is premenarchal, without a uterus and/or both ovaries, or has had a bilateral tubal ligation, has undergone the Essure procedure with confirmation of tubal blockage, or is postmenopausal. Females identified as postmenopausal for less than 2 years must have serum Follicle Stimulating Hormone (FSH) of 40 mIU/mL or greater at the Screening visit to be considered postmenopausal.

Exclusion Criteria:

1. Has tumor(s) of the lips, sinuses, salivary glands, nasopharynx, glottic larynx, subglottic larynx, or unknown primary tumor
2. Has metastatic disease (M1) Stage IV C
3. Has had prior radiation to the head and neck for any reason/condition
4. Plan to be treated with cetuximab (Erbitux®) and not cisplatin as the component of chemoradiation

5. Planned use of cisplatin as induction chemotherapy.
6. Has a history of other malignant tumors within the last 5 years, except non-melanoma skin cancer or in situ cervical carcinoma curatively excised
7. Has had a major surgical procedure, other than for HNC, or significant traumatic injury within 4 weeks prior to the initiation of RT; anticipation of need for major surgical procedure during the course of the study
8. Will have incompletely healed sites of dental extractions on first day of chemoradiation treatment
9. Has a 12-lead ECG obtained at screening visit which shows medically significant abnormality(ies) (e.g. left bundle branch block, frequent premature ventricular contractions, QTc interval prolongation > 450 msec for males and > 470 msec for females)
10. Has untreated hypertension or has hypertension under treatment meeting one of the following definitions:
 - a. Age \geq 60 years: SBP \geq 150 mmHg and/or DBP \geq 90 mmHg
 - b. Age < 60 years: SBP \geq 140 mmHg and/or DBP \geq 90 mmHg
 - c. All ages with diabetes: SBP \geq 140 mmHg and/or DBP \geq 90 mmHg

NOTE: Medical therapy for untreated hypertension may be initiated or existing treatment for hypertension may be optimized during the Screening Phase if clinically indicated. Blood pressures will then be reassessed before Day 1 to confirm eligibility. Blood pressure criteria need to be met at screening and/or prior to dosing on Day 1.

11. Has active infectious disease undergoing systemic treatment, excluding oral candidiasis
12. Has oral mucositis (of any severity) prior to initiation of radiotherapy
13. Has a diagnosis of an immunosuppressive illness or a condition requiring chronic immunosuppression
14. Has known seropositivity for HIV or hepatitis C antibody, or known to be hepatitis B surface antigen positive (testing for these serologic markers is not required for enrollment in this protocol)
15. Use of any investigational agent within 30 days of randomization
16. Is pregnant or breastfeeding
17. Has known allergies or intolerance to brilacidin, cisplatin, or carboplatin
18. Has inability to give informed consent or comply with study requirements
19. Has any other condition or prior therapy that in the opinion of the Investigator would make the patient unsuitable for the study and/or unable to comply with requirements for follow-up visits.
20. Is unwilling or unable to agree to swish and spit the study oral rinse three times per day during the study period

Test Product, Dose, and Mode of Administration:

Brilacidin (45 mg/ 15mL WFI) oral rinse tid, or placebo (15mL WFI) oral rinse tid

Efficacy and Safety Endpoints:

Primary Efficacy Endpoint

Incidence of severe OM (WHO Grade ≥ 3) experienced during radiation therapy by subjects with HNC receiving concomitant chemoradiation therapy and a cumulative radiation dose of at least 55 Gy.

Secondary Efficacy Endpoints

- Duration of severe OM (WHO Grade ≥ 3), from initial WHO Grade ≥ 3 during radiation therapy to the first WHO Grade 2 or lower OM assessment during/after radiation therapy.
- Duration of severe OM (WHO Grade ≥ 3), from initial WHO Grade ≥ 3 during radiation therapy to the last WHO Grade ≥ 3 assessment during/after radiation therapy.
- Time to onset of severe OM (WHO Grade ≥ 3).
- Incidence of severe OM (WHO Grade ≥ 3) by cumulative IMRT.

Safety Endpoints

The safety and tolerability of treatment with brilacidin will be assessed through incidence, severity and type of adverse events, including serious adverse events, and changes in clinical laboratory parameters, blood pressure, heart rate, ECOG, and body weight.

Systemic Exposure/Pharmacokinetic Endpoints

Brilacidin systemic exposure will be estimated from plasma sample concentrations; samples will be obtained from each randomized subject at weekly intervals during the CRT treatment period.

Data Analysis:

Efficacy Analyses

Full details of the statistical methodology for summary and analyses of the data collected in this study will be prepared separately from this protocol in a Statistical Analysis Plan (SAP).

The primary efficacy objective is to evaluate brilacidin compared to placebo in reducing the incidence of severe OM (defined as grade 3 or 4 on the WHO Oral Mucositis scale, WHO Grade ≥ 3) in subjects with HNC receiving concomitant chemoradiation therapy and a cumulative radiation dose of at least 55 Gy. For this comparison the Fishers Exact Test will be used.

Time to onset of severe OM (WHO Grade ≥ 3) will be assessed using the log rank test. Both a scale of days, and a scale of cumulative radiation dose delivered (Gy) will be used for the

Kaplan-Meier analysis. The log rank test will be used to compare treatment groups at time of onset of severe OM. Time to onset of ulcerative OM (WHO Grade ≥ 2) will be explored similarly.

Duration of severe OM (WHO Grade ≥ 3) is evaluated two different ways: (1) Initial instance duration of severe OM is defined as the number of days from initial WHO Grade ≥ 3 during radiation therapy until the first WHO Grade 2 or lower OM Grade occurs; (2) Overall duration of severe OM is defined as the number of days from initial WHO Grade ≥ 3 during radiation therapy to the last WHO Grade ≥ 3 assessment during/after radiation therapy. If any subject does not experience severe OM, his/her duration will be set to 0. Subjects who experience severe OM but do not resolve to WHO Grade 2 or lower will be censored at the last study visit. The effect of treatment on the duration of severe OM will be assessed using a log rank statistic. Analyses will be done using both a scale of days, and a scale of cumulative radiation dose delivered (Gy).

Safety Analysis

All safety data, demographic and baseline characteristics will be summarized descriptively through appropriate data tabulations, descriptive statistics, and categorical summaries.

Changes in blood pressure, heart rate, and hematology and clinical chemistry parameters from baseline to the end of the study will be summarized. Treatment-emergent changes from values within normal range to abnormal values in clinical laboratory parameters will be identified by means of summary and shift tables. ECOG and body weight changes from baseline to the end of the study will also be summarized.

Interim Analysis

Ad-hoc interim analyses may be conducted to support decision making concerning the current clinical study, the Sponsor's clinical development projects in general or in case of any safety concerns. Such analyses may be unblinded, and the details will be documented in the SAP.

Sample Size

The proportion of subjects experiencing severe OM (WHO Grade ≥ 3) after a total cumulative radiation dose of at least 55 Gy (and no more than 72 Gy) is unknown but expected to be approximately 75% for the placebo oral rinse treatment group, and the assumption for the active Brilacidin oral rinse treatment group is estimated to reduce to approximately 35-40%. Based on these assumptions, a sample size of 23-30 subjects per treatment group is appropriate to detect the specified difference with at least 80% power.

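### Optional: Boschloo's exact test would never have less power than the named Fisher's exact test for the primary comparison, and would typically add about 3 to 6 points with no extra patients

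*Combined protocol and SAP*

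**What the plan says.** The protocol synopsis, under Efficacy Analyses, sets the primary objective as a comparison of two proportions ("The primary efficacy objective is to evaluate brilacidin compared to placebo in reducing the incidence of severe OM") and names the test: "For this comparison the Fishers Exact Test will be used".

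Under Sample Size, the placebo rate "is unknown but expected to be approximately 75% for the placebo oral rinse treatment group". For the other arm, "the assumption for the active Brilacidin oral rinse treatment group is estimated to reduce to approximately 35-40" percent. From these it concludes that "a sample size of 23-30 subjects per treatment group is appropriate to detect the specified difference with at least 80% power". Number of Subjects Planned gives "Approximately 60 subjects with head and neck cancer receiving concurrent chemotherapy and radiotherapy", and allocation is 1:1, so about 30 per arm.

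The supplied text states no alpha, sidedness or dropout allowance, and names no other test for this comparison. Full methodology is deferred to a separate SAP, whose text is not included. Under Interim Analysis, ad-hoc looks are allowed: "Such analyses may be unblinded, and the details will be documented in the SAP".

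**The concern.** Fisher's test conditions on the total number of events, which makes it coarse in small trials: its real type I error can sit well below the nominal level. The unused error is lost power. With two binomial arms and fixed arm sizes, an unconditional exact test can recover part of it and still guarantee the level.

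Boschloo's test does this most directly. It keeps Fisher's p-value as the ranking of tables and raises the cut-off until the maximum type I error is just under alpha. Its rejection region therefore contains Fisher's. At stake is a modest amount of power in a trial of about 60 patients, available at no recruitment cost. The validity of the planned analysis is not in question.

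**Working it through.** **Inputs.** Placebo 75%, active 35-40%, 23-30 per group, about 60 in total, 1:1 (all from the synopsis). Alpha and sidedness are not given, so two-sided 5% and one-sided 5% are both shown as assumptions. Arms are written placebo v active.

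**Step 1: the plan's own figure.** The usual formula is n = [z_α√(2p̄q̄) + z_β√(p₁q₁ + p₂q₂)]² / d², with z_β = 0.842.

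- Two-sided 5%, no continuity correction. At 35%: (1.960×0.7036 + 0.842×0.6442)² / 0.40² = 23.07. At 40%: (1.960×0.6991 + 0.842×0.6538)² / 0.35² = 30.11. Rounded up, these are 24 and 31.
- One-sided 5%, with continuity correction n/4 × [1 + √(1 + 4/(nd))]². At 35%: 18.05 becomes 22.78, so 23. At 40%: 23.60 becomes 29.03, so 30.
- Exact Fisher power at one-sided 5%: 0.811 at 23 per group (35%) and 0.806 at 30 per group (40%).
- Exact Fisher power at two-sided 5%: 0.716 and 0.719 at the same points.

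So 23 and 30 are reproduced, but more than one convention leads to them or very near them. They do not settle alpha or sidedness. Pairing 23 with 35% and 30 with 40% is itself an inference.

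**Step 2: exact size and power.** Let b(x; n, p) be the binomial probability. For a rejection region R:

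- size(R) = max over π of Σ_R b(x; n₁, π) b(y; n₂, π), taken over a 1,999-point grid of π
- power(R) = Σ_R b(x; n₁, 0.75) b(y; n₂, p_active)

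Fisher's R is all tables with Fisher p ≤ 0.05. Boschloo's R is all tables with Fisher p ≤ c, where c is the largest cut-off that keeps size(R) ≤ 0.05.

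Results at 30 v 30:

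| Level | Test | Maximum size | Power, active 35% | 37.5% | 40% |
|---|---|---|---|---|---|
| Two-sided 5% | Fisher | 0.027 | 0.841 | 0.784 | 0.719 |
| Two-sided 5% | Boschloo | 0.047 | 0.889 | 0.846 | 0.793 |
| One-sided 5% | Fisher | 0.028 | 0.899 | 0.857 | 0.806 |
| One-sided 5% | Boschloo | 0.049 | 0.938 | 0.909 | 0.870 |

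The gain over 35-40% is 4.9 to 7.4 points two-sided and 4.0 to 6.4 points one-sided.

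**Step 3: other arm sizes.** All 64 pairs with 23 to 30 analysed in each arm:

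| Level | Median gain at 35 / 37.5 / 40% (points) | Range (points) |
|---|---|---|
| Two-sided 5% | 3.3 / 3.9 / 4.4 | 0.05 to 9.8 |
| One-sided 5% | 4.4 / 5.4 / 6.4 | 0.4 to 9.3 |

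Boschloo's region contained Fisher's in all 64 pairs under both conventions, and its largest size was just under 0.0500. The smallest two-sided gain is at 23 v 26 with 35% (0.8023 to 0.8028); the largest is at 23 v 23 with 40% (0.581 to 0.679).

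**Step 4: one patient away from 30 v 30.** Gain in points at 35% / 40%:

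| Arms | Two-sided 5% | One-sided 5% |
|---|---|---|
| 29 v 30 | 0.9 / 2.1 | 2.5 / 4.9 |
| 30 v 29 | 0.7 / 1.6 | 1.1 / 2.3 |
| 30 v 31 | 0.6 / 1.5 | 1.2 / 3.1 |
| 31 v 30 | 0.4 / 1.2 | 0.2 / 0.7 |

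**Step 5: the placebo rate.** At 30 v 30, active 40%, two-sided 5%, Fisher's power is 0.561, 0.719 and 0.851 for placebo rates of 70%, 75% and 80%. Boschloo's is 0.647, 0.793 and 0.899. It is higher each time, but the placebo rate moves power more than the choice of test does.

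**The case against.** Fisher's test is valid, familiar and standard for a binary Phase 2 endpoint, and the separate SAP may already fix alpha, sidedness and the two-sided definition. The 30 v 30 gain is also a favourable figure at two-sided 5%, because a single patient's imbalance leaves only about 0.4 to 2.1 points. The plan is for approximately 60 subjects and the endpoint refers to those receiving at least 55 Gy, so exactly 30 v 30 analysed is one outcome among many. All of this stands, which is why the point is optional and why the medians and ranges matter more than the 30 v 30 figure.

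It is also true that Boschloo's test brings a choice of its own. Software that doubles the one-sided p-value fails to reject everywhere that two-sided Fisher does in 26 of the 64 pairs. The never-less-power property belongs to the version ordered by the two-sided Fisher p-value, so the definition has to be written down.

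Two stronger readings are tempting, and neither is supported:

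- **That the 80% power claim fails under Fisher's test.** This needs two-sided 5%, which the supplied text does not state. At one-sided 5% Fisher meets 80% at both pairings. Nor would Boschloo rescue the claim at two-sided 5%: it gives 0.793 at 23 per group with 35% and 0.793 at 30 per group with 40%.
- **That the change is worth a fixed number of patients.** With equal arms, Fisher needs about 33 per group (two-sided) or 34 (one-sided) to match Boschloo at 30. But Fisher's power is irregular in the arm sizes: at two-sided 5% and 35%, one more placebo patient (31 v 30) lifts it from 0.841 to 0.883. No stable patient equivalent follows.

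**Conclusion.** The point holds as an optional, low-cost improvement. For arms of 23 to 30, Boschloo's test with the matching Fisher ordering keeps the 5% level and never has less power than the named test. Under the plan's own rates the typical gain is about 3 to 6 points. It can approach 10, and it can be under 1 point for some arm sizes: at 35%, 12 of the 64 pairs two-sided and 2 of 64 one-sided.

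The sizes rest on placebo 75% and active 35-40%, on the two assumed alpha conventions, and on treating the 64 arm-size pairs as a plausible spread, since the supplied text gives no dropout rate. The direction does not depend on the assumed rates, because one rejection region contains the other.

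**What to change.** Before any unblinding, including any ad-hoc interim analysis:

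1. Name Boschloo's exact test as the primary test and keep Fisher's exact test as a sensitivity analysis.
2. State alpha and sidedness. If the test is two-sided, define it as ordering tables by the two-sided Fisher p-value, not as a doubled one-sided p-value, and name the software or code.
3. State power for the chosen test at that alpha and sidedness. At 30 per group over 35-40%, Boschloo gives 0.79-0.89 (two-sided 5%) or 0.87-0.94 (one-sided 5%). If Fisher is kept, the matching figures are 0.72-0.84 or 0.81-0.90.

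The cost is protocol and SAP wording, with no extra patients. The downsides are a less familiar test, the need to fix its definition and software in advance, and a gain that may turn out negligible for the arm sizes actually analysed.

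### At an assumed two-sided 0.05, the primary Fisher's exact test has about 72% power for 75% vs 40%, below the stated 80%; a CMH test stratified by planned cisplatin schedule gives about 79-84%, mostly by avoiding Fisher's conservatism

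*Combined protocol and SAP*

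**What the plan says.** The Efficacy Analyses part of the synopsis sets the primary comparison of severe oral mucositis (WHO grade 3 or 4) between arms: "For this comparison the Fishers Exact Test will be used". It names no stratum or covariate.

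Inclusion Criterion 5 requires each subject to "Have a plan to receive a standard cisplatin chemotherapy regimen administered weekly" or about every 21 days, so the planned schedule is known for everyone before randomisation. On allocation, Design and Methodology says only: "Eligible subjects will be randomized to receive one of the following study drug regimens during participation in the study (1:1 ratio").

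The Sample Size paragraph takes the severe mucositis rate as "expected to be approximately 75% for the placebo oral rinse treatment group", while "the active Brilacidin oral rinse treatment group is estimated to reduce to approximately 35-40" per cent. It concludes that "a sample size of 23-30 subjects per treatment group is appropriate to detect the specified difference with at least 80% power". The planned total is "Approximately 60 subjects with head and neck cancer receiving concurrent chemotherapy and radiotherapy", or 30 per arm.

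Full statistical methodology "will be prepared separately from this protocol in a Statistical Analysis Plan (SAP"). The text available states no alpha, no sidedness, no split of subjects by schedule and no mucositis rate by schedule.

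**The concern.** Two features of the named test matter in a trial of this size.

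First, Fisher's exact test is conservative. With 30 per arm the attainable p-values are coarse and the actual type I error falls well below the nominal level. A sample size that gives 80% power under a normal-approximation formula need not give 80% under this test.

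Second, the test uses no baseline information. Cisplatin schedule is recorded for every subject and could plausibly relate to mucositis. If the arms differ by chance in schedule mix, the crude comparison cannot adjust for it, and any later adjustment would be post hoc.

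At stake are the power the sponsor believes it has at the less favourable end of its own assumption, and how clearly a single small trial can be read.

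**Working it through.** **Inputs.** From the documents: 75% on placebo, 35-40% on brilacidin, 23-30 per group, about 60 in total, two cisplatin schedules. Assumed: two-sided 0.05; all 30 per arm analysed; schedule split 50:50 or 35:65; placebo rates differing by 0, 20 or 30 points between schedules; simple randomisation.

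**1. The plan's own figure.** Pooled normal formula: n = [1.960·√(2p̄q̄) + 0.8416·√(p₁q₁ + p₂q₂)]² / (p₁ - p₂)².

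- 75% vs 35%: p̄ = 0.55, so (1.960·√0.495 + 0.8416·√0.415)² / 0.16 = 23.1, rounded up to 24.
- 75% vs 40%: p̄ = 0.575, so (1.960·√0.48875 + 0.8416·√0.4275)² / 0.1225 = 30.1, rounded up to 31.

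The arcsine formula, n = 2·[2.8016 / (2·(asin√p₁ - asin√p₂))]², gives exactly 23 and 30. The continuity-corrected formula at one-sided 0.05 also gives 23 and 30. The stated range therefore reproduces, but more than one route leads to it and the documents do not say which was used.

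**2. Power of the named test.** Power = Σᵢ Σⱼ Bin(i; n, p₁)·Bin(j; n, p₂)·1[p-value ≤ 0.05], by full enumeration.

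| n per arm | Rates | Fisher, two-sided 0.05 | Fisher, one-sided 0.05 | Pearson, two-sided 0.05 |
|---|---|---|---|---|
| 23 | 75% vs 35% | 71.6% | 81.1% | 81.1% |
| 30 | 75% vs 40% | 71.9% | 80.6% | 80.2% |
| 30 | 75% vs 35% | 84.1% | 89.9% | 89.8% |

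Two-sided Fisher is still at 79.7% for 75% vs 40% with 36 per arm.

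One outcome shows the mechanism. With 23/30 vs 15/30, the Pearson statistic is z = (8/30) / √(0.6333·0.3667·2/30) = 2.14, p = 0.032. Fisher's two-sided p is 2·Σₓ₌₂₃³⁰ C(38,x)·C(22,30-x)/C(60,30) = 0.060.

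**3. Separating conservatism from stratification.** Simulated trials at 30 per arm, 50:50 schedule split, two-sided 0.05. The rates by schedule average to 75% vs 40% in every row. The CMH statistic, without continuity correction, is [Σ(aₛ - E aₛ)]² / ΣVar(aₛ), referred to 3.84.

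| Placebo rates by schedule | Active rates by schedule | Fisher | Pearson, unstratified | CMH by schedule |
|---|---|---|---|---|
| 75%, 75% | 40%, 40% | 71.8% | 80.1% | 79.5% |
| 85%, 65% | 50%, 30% | 71.9% | 80.2% | 81.3% |
| 90%, 60% | 55%, 25% | 71.8% | 80.2% | 83.8% |

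- Fisher to Pearson, no use of schedule: 80.1 - 71.8 = 8.3 points.
- Pearson to CMH, the effect of stratifying: about -0.6, +1.1 and +3.6 points. With a 35:65 split: -0.6, +0.7 and +2.6.
- Actual size: Fisher 2.5-2.7%; CMH 4.9-5.1%, with up to 5.5% in smaller runs of 10,000 trials.

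**4. Like for like.** An exact conditional test stratified by schedule, against Fisher, gains 2.2-5.2 points at 75% vs 40% for schedule odds ratios of 1-3, 8.6 at 5 and 11.4 at 8. For scale, 90% vs 60% is an odds ratio of (0.9/0.1)/(0.6/0.4) = 6.

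**5. Chance imbalance.** A 20-point difference in schedule mix is 6 subjects in 30. With independent X ~ Bin(30, w) in each arm, P(|X_A - X_B| ≥ 6) = 15.5% at w = 0.50 and 13.6% at w = 0.35.

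**The case against.** A fair defence runs as follows. Fisher's test is valid and exact, and it is a conventional choice for a phase 2 trial of 60. The documents treat the two schedules as equally acceptable and never say that schedule is prognostic; tumour site or planned radiation dose might be as good a stratifier. Power is adequate at 75% vs 35%, and at 75% vs 40% if one-sided 0.05 was meant. The separate SAP may already hold a stratified or supportive analysis.

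Most of this stands, and it limits the point. A reader might infer that ignoring cisplatin schedule is what costs 8-12 points of power. The documents do not support that. With no schedule effect the gap to Fisher is still about 8 points and stratifying loses slightly. For schedule alone to explain a loss of that size, like for like, would take an odds ratio of about 5-8, for which the documents give no basis. A reader might also infer that chance imbalance biases the test. Under randomisation it does not inflate type I error: Fisher's simulated size stays near 2.5%. Nor can one say that stratified randomisation or an adjusted analysis is absent, since the SAP text is not available.

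The mismatch between the named test and the stated power survives at two-sided 0.05. The case for the CMH test also does not need schedule to be prognostic: at zero effect it gives up about 0.6 points to Pearson and still exceeds Fisher by about 8.

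**Conclusion.** The point holds as a moderate one. With 30 per arm and an assumed two-sided 0.05, the named test gives about 72% power for 75% vs 40%, short of the stated minimum of 80%. There is no shortfall with 30 per arm at 75% vs 35% (84.1%), nor at one-sided 0.05 for 75% vs 40% (80.6%). A CMH test stratified by planned schedule gives about 79-84% at about 5% size.

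Of that gain, about 8 points are Fisher's conservatism and about -1 to +4 points are stratification, over an assumed 0-30 point difference in placebo rates between schedules. Stratifying also deals with a schedule imbalance of 20 points or more, which has about a 14-16% chance under simple randomisation. That benefit is to precision and interpretation.

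The result rests on the assumed alpha and sidedness, the assumed schedule split and effect, and all 60 subjects being analysed.

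**What to change.** Before any unblinding, including any unblinded ad hoc interim analysis of the kind the synopsis allows, amend the SAP in one of two ways:

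- **Preferred.** Make the CMH test stratified by planned cisplatin schedule (two strata, by the plan recorded at entry) the primary test. Report the stratified risk difference with its confidence interval, and keep Fisher's exact test as a sensitivity analysis.
- **If Fisher stays primary.** State alpha and sidedness, restate the power the test delivers at 30 per arm for both ends of the 35-40% range, and pre-specify the CMH test as supportive.

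State alpha and sidedness in either case. The cost is SAP wording, with no added subjects. The downside is small: the CMH test relies on a large-sample approximation, so guaranteed control of size is exchanged for approximate control.
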